6.6.3.1 Diagnosis and Management of Non-overdose Hepatic ECIs

HCC participants are at risk for a range of complications that can cause hepatic laboratory abnormalities with or without clinical decompensation. Those with a history of chronic HCV or HBV infection also have the potential to experience virologic flares. Immune-related hepatitis has been observed in approximately 1% of participants who received pembrolizumab.

For dose interval modification, refer to Sections 6.6.1 and 6.6.2. Guidance related to the diagnosis and management of hepatic ECIs is located in [Table 16](#).

Table 16 Management of Hepatic ECIs

Event	Diagnosis	Management
Hepatitis B consider flare or change in HBV immunologic status	Rapid elevation of ALT to $>5 \times$ ULN and/or $>3 \times$ baseline	
Interrupt intervention for up to 12 weeks. Start antiviral therapy or check for compliance if HBV is detectable. Measure safety labs for AST, ALT, ALP, Tbil, Dbil, and INR on weekly basis. Measure HBsAg and HBV DNA on weekly basis (if detected at the time of onset of ECI). Evaluate the following every 2 to 3 weeks:
 
 • anti-HBe, HBe antigen, anti-HBs, and HBV DNA levels (if not detected at the onset of ECI) 
Restart intervention only if ALT returns to normal or Grade 1 (if normal at baseline), or to baseline grade (if Grade 2 at baseline) within 12 weeks, and the participant is clinically stable; otherwise, the participant should be permanently discontinued.

Hepatitis C exacerbation in participants with HCV RNA positive	Rapid elevation of ALT to $>5 \times$ ULN and/or $>3 \times$ baseline	
Interrupt intervention for up to 12 weeks. Assess use of injection or inhalation drugs. Recheck HCV genotype at the time of relapse of HCV RNA to rule out new infection. Measure safety labs for AST, ALT, ALP, Tbil, Dbil, and INR on weekly basis. Measure HCV RNA levels every 2 weeks. Please discuss risk benefit with Sponsor prior to starting HCV antiviral therapy. Restart intervention only if ALT returns to normal or Grade 1 (if normal at baseline), or to baseline grade (if Grade 2 at baseline) within 12 weeks, and the participant is clinically stable; otherwise, the participant should be permanently discontinued.

Relapse of HCV infection for participants with successfully treated or new HCV infection	If HCV RNA was TND at baseline, and now has confirmed detectable HCV RNA (2 specimens, 1 week apart)	
Interrupt intervention for up to 12 weeks. Assess use of injection or inhalation drugs. Recheck HCV genotype at the time of relapse of HCV RNA to rule out new infection. Measure safety labs for AST, ALT, ALP, Tbil, Dbil, and INR on weekly basis. Measure HCV RNA levels every 2 weeks. Please discuss risk benefit with Sponsor prior to starting HCV antiviral therapy. Restart intervention only if ALT returns to normal or Grade 1 (if normal at baseline), or to baseline grade (if Grade 2 at baseline) within 12 weeks, and the participant is clinically stable; otherwise, the participant should be permanently discontinued.

Event	Diagnosis	Management
Immune-related Hepatitis	
If any of the HECI criteria are met as defined in the protocol Section 8.4.7
 
Note:
 
Immune-related hepatitis is a diagnosis made after excluding other possible etiologies such as viral flare, biliary or vascular obstruction, infection, medications, and alcohol use usually immune-related hepatitis response to dechallenge and/or steroids and reoccurs with rechallenge.
	
Interrupt intervention for up to 12 weeks. Start IV corticosteroid 60 mg/day of prednisone or equivalent followed by oral corticosteroid. Monitor with biweekly laboratory tests, including AST, ALT, Tbil, Dbil, ALP, and INR.
 
Restart intervention only if:
 
 Abnormal laboratory values resolve to Grade ≤ 1 or baseline (if abnormal at baseline) Taper steroid over 28 days Steroid treatment is tapered to prednisone < 10 mg/day or equivalent 
Permanently Discontinue intervention if:
 
 Laboratory abnormalities do not resolve within 3 weeks Steroids cannot be lowered to ≤ 10 mg/day (or prednisone equivalent) within 12 weeks Decompensation to CP-C status
Other Causes	
Rule out infection with blood, urine, and ascites culture – antibiotics should be started if infection is found.
 
If total bilirubin is elevated, imaging should be obtained to rule out vascular compromise, biliary obstruction, and/or tumor progression by imaging.
 
Ruled out alcohol use and hepatotoxic drugs including herbal and alternative medications.
	
Restart intervention only if laboratory values have returned to Grade 1 or baseline (if normal or Grade 1 at start) or to baseline grade within 3 weeks.
 
If biliary obstruction is present, consultation with a gastroenterologist and/or an interventional radiologist should be obtained to see if the obstruction may be relieved.

Abbreviations: ALP=alkaline phosphatase; ALT=alanine aminotransferase; AST=aspartate aminotransferase; CP-C=Child-Pugh Grade C; Dbil=direct bilirubin; DNA=deoxyribonucleic acid; HBs=hepatitis B surface; HBeAg=hepatitis B e antigen, HBV=hepatitis B virus; INR=international normalized ratio; IV=intravenous; Tbil=total bilirubin; TND=target not detected.

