Diarrhea/Colitis	Grade 2 or 3	Withhold	
 Administer corticosteroids (initial dose of 1 to 2 mg/kg prednisone or equivalent) followed by taper 	
 Monitor participants for signs and symptoms of enterocolitis (ie, diarrhea, abdominal pain, blood or mucus in stool with or without fever) and of bowel perforation (ie, peritoneal signs and ileus) Participants with \geqGrade 2 diarrhea suspecting colitis should consider GI consultation and performing endoscopy to rule out colitis Participants with diarrhea/colitis should be advised to drink liberal quantities of clear fluids. If sufficient oral fluid intake is not feasible, fluid and electrolytes should be substituted via IV infusion
	Recurrent Grade 3 or Grade 4	Permanently discontinue		

irAEs	Toxicity Grade (CTCAE v5.0)	Action With Pembrolizumab Monotherapy, Coformulations or IO Combinations	Corticosteroid and/or Other Therapies	Monitoring and Follow-up
AST or ALT Elevation or Increased Bilirubin	Grade 2 ^a	Withhold	
 Administer corticosteroids (initial dose of 0.5 to 1 mg/kg prednisone or equivalent) followed by taper 	
 Monitor with liver function tests (consider weekly or more frequently until liver enzyme value returned to baseline or is stable)
	Grade 3 ^b or 4 ^c	Permanently discontinue	
 Administer corticosteroids (initial dose of 1 to 2 mg/kg prednisone or equivalent) followed by taper 	
T1DM or Hyperglycemia	New onset T1DM or Grade 3 or 4 hyperglycemia associated with evidence of β -cell failure	Withhold ^d	
 Initiate insulin replacement therapy for participants with T1DM Administer antihyperglycemic in participants with hyperglycemia 	
 Monitor participants for hyperglycemia or other signs and symptoms of diabetes
Hypophysitis	Grade 2	Withhold	
 Administer corticosteroids and initiate hormonal replacements as clinically indicated 	
 Monitor for signs and symptoms of hypophysitis (including hypopituitarism and adrenal insufficiency)
	Grade 3 or 4	Withhold or permanently discontinue ^d		

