AE(s)=adverse event(s); ALT=alanine aminotransferase; AST=aspartate aminotransferase; CTCAE=Common Terminology Criteria for Adverse Events; DRESS=Drug Rash with Eosinophilia and Systemic Symptom; GI=gastrointestinal; IO=immuno-oncology; ir=immune related; IV=intravenous; SJS=Stevens-Johnson Syndrome; T1DM=type 1 diabetes mellitus; TEN=Toxic Epidermal Necrolysis; ULN=upper limit of normal.

Note: Non-irAE will be managed as appropriate, following clinical practice recommendations.

^a AST/ALT: >3.0 to 5.0 x ULN if baseline normal; >3.0 to 5.0 x baseline, if baseline abnormal; bilirubin: >1.5 to 3.0 x ULN if baseline normal; >1.5 to 3.0 x baseline if baseline abnormal

^b AST/ALT: >5.0 to 20.0 x ULN, if baseline normal; >5.0 to 20.0 x baseline, if baseline abnormal; bilirubin: >3.0 to 10.0 x ULN if baseline normal; >3.0 to 10.0 x baseline if baseline abnormal

^c AST/ALT: >20.0 x ULN, if baseline normal; >20.0 x baseline, if baseline abnormal; bilirubin: >10.0 x ULN if baseline normal; >10.0 x baseline if baseline abnormal

^d The decision to withhold or permanently discontinue pembrolizumab monotherapy, coformulations or IO combinations is at the discretion of the investigator or treating physician. If control achieved or \leq Grade 2, pembrolizumab monotherapy, coformulations or IO combinations may be resumed.

^e Events that require discontinuation include, but are not limited to: encephalitis and other clinically important irAEs (eg, vasculitis and sclerosing cholangitis).

Dose Modification and Toxicity Management of Infusion Reactions Related to Pembrolizumab

Pembrolizumab may cause severe or life-threatening infusion-reactions including severe hypersensitivity or anaphylaxis. Signs and symptoms usually develop during or shortly after drug infusion and generally resolve completely within 24 hours of completion of infusion. Dose modification and toxicity management guidelines on pembrolizumab associated infusion reaction are provided in [Table 15](#).

Table 15 Pembrolizumab Infusion Reaction Dose Modification and Treatment Guidelines

NCI CTCAE Grade	Treatment	Premedication at Subsequent Dosing
Grade 1 Mild reaction; infusion interruption not indicated; intervention not indicated	Increase monitoring of vital signs as medically indicated until the participant is deemed medically stable in the opinion of the investigator	None

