8.4.7 Events of Clinical Interest

Selected serious and nonserious AEs are also known as ECIs and must be reported to the Sponsor.

Events of clinical interest for this study include:

1. An overdose of Sponsor's product, as defined in Section 8.5.
2. All cohorts except HCC-specific expansion cohorts:
An elevated AST or ALT lab value that is greater than or equal to 3X the upper limit of normal and an elevated total bilirubin lab value that is greater than or equal to 2X the upper limit of normal and, at the same time, an alkaline phosphatase lab value that is less than 2X the upper limit of normal, as determined by way of protocol-specified laboratory testing or unscheduled laboratory testing.*

*Note: These criteria are based upon available regulatory guidance documents. The purpose of the criteria is to specify a threshold of abnormal hepatic tests that may require an additional evaluation for an underlying etiology. The study site guidance for assessment and follow up of these criteria can be found in the Investigator Study File Binder (or equivalent).

3. HCC-specific expansion cohort, Arm 2 Part II:
Hepatic ECIs include any of the following events if the events are considered not due to disease progression or TACE as judged by the investigator. All of these events (if not associated with disease progression under study) will require holding study treatment, notification of the event(s) to the Sponsor within 24 hours after awareness via electronic media or paper.

For dose interval modification, refer to Section 6.6.1 (V937) and 6.6.2 (pembrolizumab). For guidance related to the diagnosis and management of hepatic ECIs, refer to Section 6.6.3.

- ALT:
 - Among participants with Baseline ALT $<2 \times$ ULN: ALT $\geq 5 \times$ ULN
 - Among participants with Baseline ALT $\geq 2 \times$ ULN: ALT $>3 \times$ the Baseline level
 - ALT >500 U/L regardless of baseline level

- Total Bilirubin:
 - Total bilirubin >3.0 mg/dL
- Regardless of laboratory values, hepatic decompensation diagnosed clinically, including:
 - New onset clinically detectable ascites requiring intervention for >3 days
 - Hepatic encephalopathy
 - Gastrointestinal bleeding suggestive of portal hypertension (eg, esophageal or gastric varices)

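### For immune-related hepatitis in Cohort D, Tables 14 and 16 both apply and give different steroid and stopping instructions, with no clear statement of which governs

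*Combined protocol and SAP*

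**What the plan says.** Protocol Section 6.6.2, Table 14 covers immune-related AST/ALT elevation or increased bilirubin for the whole study. It has no exception for hepatocellular carcinoma. At Grade 2, pembrolizumab is withheld and the instruction is "Administer corticosteroids (initial dose of 0.5 to 1 mg/kg prednisone or equivalent) followed by taper". At Grade 3 or 4, pembrolizumab is permanently discontinued and the instruction is "Administer corticosteroids (initial dose of 1 to 2 mg/kg prednisone or equivalent) followed by taper". The Grade 3 footnote begins "AST/ALT: >5.0 to 20.0 x ULN, if baseline normal". Liver tests are suggested weekly or more often.

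Section 6.6.3.1, Table 16 has its own row for immune-related hepatitis. Its trigger is "If any of the HECI criteria are met as defined in the protocol Section 8.4.7", and the list of hepatic ECIs in Section 8.4.7 is headed "HCC-specific expansion cohort, Arm 2 Part II". The row interrupts treatment for up to 12 weeks, then says "Start IV corticosteroid 60 mg/day of prednisone or equivalent followed by oral corticosteroid" and "Monitor with biweekly laboratory tests, including AST, ALT, Tbil, Dbil, ALP, and INR". Restart is allowed once laboratory values recover and the steroid is below 10 mg/day. Permanent discontinuation applies if, among other things, "Laboratory abnormalities do not resolve within 3 weeks", or if the steroid cannot be brought to 10 mg/day or less within 12 weeks.

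**The concern.** A Cohort D participant whose hepatitis is judged immune-related and meets a HECI criterion comes under both tables. One sets the steroid by weight and grade; the other fixes it. One ends pembrolizumab at Grade 3 or 4; the other pauses treatment and may resume it. Two sites could treat the same event differently, and both would be following the protocol.

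The steroid difference is a safety matter. The stopping difference also reaches the analysis, because discontinuing a study intervention due to an AE is a primary endpoint for Arm 2 (Section 3). The same event could count as a discontinuation under one table and as a temporary interruption under the other.

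**Working it through.** **1. When does 60 mg/day satisfy Table 14?** For a Table 14 range of lo to hi mg/kg and body weight W, 60 mg is inside when lo × W ≤ 60 ≤ hi × W, that is, when 60/hi ≤ W ≤ 60/lo.

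- Grade 2 (0.5 to 1 mg/kg): 60/1 = 60 kg to 60/0.5 = 120 kg.
- Grade 3-4 (1 to 2 mg/kg): 60/2 = 30 kg to 60/1 = 60 kg.

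| Weight | Grade 2 range | 60 mg is | Grade 3-4 range | 60 mg is |
|---|---|---|---|---|
| 50 kg | 25-50 mg | above | 50-100 mg | inside |
| 70 kg | 35-70 mg | inside | 70-140 mg | below |
| 130 kg | 65-130 mg | below | 130-260 mg | below |

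Only at exactly 60 kg does 60 mg satisfy both grade bands.

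**2. Can both grade bands meet a HECI criterion?** Compare Section 8.4.7 with the Table 14 footnotes.

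- Normal baseline ALT: the HECI trigger is 5 × ULN or more. Table 14 Grade 2 ends at 5 × ULN, so an ALT-triggered event is Grade 3 or higher, apart from a value of exactly 5 × ULN.
- Baseline ALT of 2 × ULN or more, which Table 8 admits up to 5 × ULN: the trigger is above 3 × baseline. Table 14 Grade 2 is above 3 and up to 5 × baseline, so the whole Grade 2 band triggers Table 16.
- Bilirubin above 3.0 mg/dL: if the ULN is 1.2 mg/dL (assumed), 3.0/1.2 = 2.5 × ULN, which is Grade 2 with a normal baseline. If the ULN is 1.0 mg/dL, anything above 3.0 mg/dL is Grade 3.

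Both bands can be reached in Cohort D.

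**3. Stopping rules side by side.** For an event at 6 × ULN with a normal baseline (Grade 3), Table 14 requires permanent discontinuation of pembrolizumab. Table 16 requires interruption and permits restart if its conditions are met. If the participant restarts, the event is a discontinuation under the first table and not under the second.

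**4. Size.** Section 6.6.3.1 gives immune-related hepatitis as about 1% of pembrolizumab recipients. Cohort D has 30 of 185 planned participants (Section 9.9). At 1%, the expected number of cases is 30 × 0.01 = 0.3, and the chance of at least one is 1 − 0.99^30 = 0.26. One reclassified participant moves the cohort's discontinuation proportion by 1/30 = 3.3 percentage points. The documents give no rate for this combination in hepatocellular carcinoma.

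**5. Smaller points in the same Table 16 row.**

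- Neighbouring rows say weekly or every 2 weeks; this row alone says biweekly. If that means every 2 weeks, tests fall at weeks 2 and 4, on either side of the 3-week limit. If it means twice a week, there is no difficulty.
- Restart needs a dose below 10 mg/day, but discontinuation applies only if 10 mg/day or less cannot be reached. A participant at exactly 10 mg/day at week 12 meets neither condition.

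**The case against.** The best reply is that the protocol does route the reader. Sections 6.6.3.1 and 8.4.7 send dose interval modification to Sections 6.6.1 and 6.6.2, and diagnosis and management of hepatic ECIs to Section 6.6.3 and Table 16. A site could fairly conclude that Table 16 governs the steroid. This does not settle the matter, because each table contains both a steroid instruction and a hold or discontinue instruction.

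Section 7.1 might also be cited. It adopts every permanent-discontinuation rule in Section 6.6, which would favour Table 14 on stopping. But Table 16 is part of Section 6.6 too, and its restart provision would then have no effect at Grade 3 or 4. Section 7.1 also lists ALT above 20 × ULN as a separate HECI stopping reason. The rule in Section 6.6.6.1 to follow the most conservative adjustment concerns several toxicities in Arm 2 Part I, not two tables for one event.

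Other objections stand and limit the point:

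- A reader might infer that most participants would get a different dose. The documents do not support this, since they give neither weights nor a grade mix. With weights assumed normal (mean 70 kg, SD 15 kg), 60 mg is outside the Table 14 range in 25% at Grade 2 and 75% at Grade 3-4. With means of 60 to 85 kg and SDs of 12 to 18 kg, the shares are 2% to 50% and 51% to 98%. In the 70 kg case, more than half of events fall outside only if the Grade 3-4 share p satisfies 0.25(1 − p) + 0.75p > 0.5, that is, p > 0.5.
- Table 16 does not apply to hepatitis of any grade, only to events meeting a HECI criterion.
- The 3-week limit is not necessarily left unread. Section 8.3.6 asks for repeat tests of clinically significant abnormal values, and biweekly may mean twice a week.
- The starting steroid dose does not itself drive discontinuation. The link to the endpoint runs only through the stopping rules.

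**Conclusion.** The contradiction is real but narrow. For a Cohort D participant with immune-related hepatitis meeting a HECI criterion, the two tables give different instructions without clear precedence. The steroid rules diverge at Grade 3-4 above 60 kg and at Grade 2 below 60 kg or above 120 kg; for other weights of 30 kg or more, 60 mg/day fits the Table 14 range. This rests on arithmetic from the tables and needs no weight assumption. The stopping rules diverge at Grade 3 or 4 regardless of weight and can change an Arm 2 primary endpoint count.

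It would be tempting to extend this to all liver-injection cohorts. Section 6.6.3 does head its assessment as being for all participants, but the hepatic ECI list that triggers Table 16 belongs to the hepatocellular carcinoma cohort, so reach beyond Cohort D is uncertain. The low expected number of cases and the decision to discontinue the study limit the practical effect. The biweekly wording and the 10 mg/day mismatch are minor. The passages should still be reconciled, because they give conflicting instructions for a safety event.

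**What to change.** The sponsor should reconcile Tables 14 and 16 for immune-related hepatitis, covering both the steroid instruction and the discontinue or restart rule, or add a sentence saying which table governs a HECI in Cohort D. In the same Table 16 row, it should state what biweekly means and reconcile the below-10 and at-most-10 mg/day limits. Which dose, interval and stopping rule are right is for the sponsor; no view is taken here.

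The cost is an edit to one or two table rows and a precedence sentence. The design, sample size and analysis methods do not change. For any such event already recorded, the sponsor should note which table the site followed, so that the discontinuation count can be read correctly.

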6.6.4 Dose Administration/Escalation

6.6.4.1 Dose Administration (Preparation)

Details on preparation and administration of V937 (and pembrolizumab) are provided in the appropriate Pharmacy/Procedures Manual.

6.6.5 Definition of Dose-limiting Toxicity for Arm 2 Part I (mTPI Escalation)

Dose-limiting toxicities are used in Arm 2 Part I to guide dose escalation and de-escalation decisions for the mTPI design (see Section 4.3.1.3). The DLT window of observation will be during Cycle 1.

All toxicities will be graded using NCI-CTCAE v5.0 based on the investigator assessment.

The occurrence of any of the following toxicities during Cycle 1 will be considered a DLT, if assessed by the investigator to be possibly, probably, or definitely related to study intervention administration.

1. Grade 4 nonhematologic toxicity (not laboratory).
2. Grade 4 hematologic toxicity lasting ≥ 7 days except for thrombocytopenia or febrile neutropenia:
 - \geq Grade 3 thrombocytopenia associated with clinically significant bleeding of any duration, or
 - Any grade of febrile neutropenia
3. Any nonhematologic AE \geq Grade 3 in severity should be considered a DLT, with the following exceptions: Grade 3 fatigue lasting ≤ 3 days; Grade 3 diarrhea, nausea, or vomiting without use of anti-emetics or anti-diarrheals per SOC; clinically asymptomatic Grade 3 elevations of amylase or lipase without any imaging evidence suggestive of possible/probable etiology; Grade 3 rash without use of corticosteroids or anti-inflammatory agents per SOC.
4. Any Grade 3 or Grade 4 nonhematologic laboratory value if:
 - Clinically significant medical intervention is required to treat the participant, or
 - The abnormality leads to hospitalization, or
 - The abnormality persists for >1 week, or
 - The abnormality results in a DILI (see Section 8.4.7 for criteria).Exceptions: Clinically nonsignificant, treatable, or reversible laboratory abnormalities including liver function tests, uric acid, etc.
5. Prolonged delay (>2 weeks) in initiating Cycle 2 due to intervention-related toxicity.
6. Any intervention-related toxicity that causes the participant to discontinue intervention during Cycle 1.
7. Missing the following number of ITu V937 doses as a result of drug-related AE(s) during the first cycle:
 - Visceral tumor, dose escalation: missing 1 dose of V937
8. Grade 5 toxicity.

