5.1.3 Arm 2 Part I: Visceral Lesion Dose Escalation and Confirmation

23. Has a histologically-confirmed advanced/metastatic solid tumor that has progressed on all treatment known to confer clinical benefit. Solid tumors of any type are eligible for enrollment with exception noted below.

Note: HCC tumors are excluded from the visceral dose escalation cohort.

24. Has metastatic liver lesion(s) not exceeding one-third of the total liver volume AND has a minimum of one injectable liver lesion with the following criteria:

- Accessible for image-guided injection and biopsy via ultrasound guidance or cross-sectional imaging (CT/MRI)

Note: If planning use of CT fluoroscopy for visceral lesion injections, must check that the participant has a CrCl ≥ 60 mL/min within 12 hours prior to procedure.

- lesion(s) must be ≥ 1 cm in longest diameter and ≤ 10 cm in longest diameter

Refer to Section 5.1.1 for additional inclusion criteria that apply to all tumor cohorts

5.1.4 **Arm 2 Part II: Visceral Cohort Expansion**

5.1.4.1 **Specific Inclusion Criteria for Cohort D: Hepatocellular Carcinoma**

25. Has advanced HCC following progression on, or intolerance to, sorafenib or lenvatinib with no curative options.
26. Has diagnosis of HCC confirmed by radiology, histology, or cytology (fibrolamellar and mixed hepatocellular/cholangiocarcinoma subtypes not eligible for enrollment).
 - a. Radiologic diagnosis is defined as: evidence of liver cirrhosis and a liver mass measuring at least 1 cm with characteristic vascularization (intense enhancement in hepatic arterial-dominant phase and contrast washout in late portal venous phase) on triphasic CT or MRI scan.
27. Has Child-Pugh Class A score (see Appendix 9).
28. If a participant has a history of HCV infection, then the participant must have been successfully treated for this condition, which is defined as SVR12. Eligible participants must wait for a period of ≥ 4 weeks between achievement of SVR12 and start of study drug(s). (See Section 6.6.3)
29. If participant has a known history of chronic hepatitis B infection and/or exposure and has received treatment with anti-hepatitis B therapy. (See Section 6.6.3)

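### In the Part I DLT definition (6.6.5), the laboratory exception in item 4 cancels that item's own triggers, and item 3 counts the same events without it

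*Combined protocol and SAP*

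**What the plan says.** All of the following is in 6.6.5 unless noted.

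- **Lead-in.** Any single item is enough, provided the investigator judges the event related: "The occurrence of any of the following toxicities during Cycle 1 will be considered a DLT".
- **Item 1.** It sets laboratory values aside: "Grade 4 nonhematologic toxicity (not laboratory").
- **Item 3.** It counts any nonhematologic AE of Grade 3 or higher, subject to listed exceptions. It has no laboratory limit, and one of its exceptions is itself a laboratory finding: "clinically asymptomatic Grade 3 elevations of amylase or lipase", where imaging suggests no cause.
- **Item 4.** It counts a Grade 3 or 4 nonhematologic laboratory value if one of four triggers is met. One trigger is "Clinically significant medical intervention is required to treat the participant". Two others are hospitalization and persistence beyond one week. The last is "The abnormality results in a DILI (see Section 8.4.7 for criteria").
- **Item 4, closing sentence.** "Exceptions: Clinically nonsignificant, treatable, or reversible laboratory abnormalities including liver function tests, uric acid, etc".

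Section 10.3.2 makes an abnormal laboratory result an AE when the investigator considers it clinically significant. Section 4.1.2 ends dose-finding once 14 participants have been treated at a dose. Section 9.6.2 calls for the DLT rate at the RP2D with a 90% credible interval from a Beta(1,1) prior.

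**The concern.** DLT is a primary endpoint of Arm 2 and drives the mTPI decisions. Part I injects liver metastases directly, so changes in liver tests are foreseeable, and the exception names exactly those tests.

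Two faults combine. Inside item 4, the same ALT rise can qualify because it needed treatment and be excused because it was treatable. Between items, item 3 counts a clinically significant Grade 3 or 4 laboratory AE whether or not it was treatable or reversible, and no sentence says whether item 4 is meant to limit item 3 for laboratory values. A site that takes item 4 as the laboratory rule can record no DLT where a site applying item 3 literally records one. The reported DLT rate then depends partly on which item a site turned to.

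**Working it through.** **1. Triggers against the exception in item 4**

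| Trigger | How the exception can cancel it |
|---|---|
| Needs clinically significant treatment | The value was *treatable* |
| Lasts more than one week | It later resolved, so it was *reversible* |
| Results in DILI | The DILI criteria are liver tests, which the exception names |
| Leads to hospitalization | Cancelled in most cases, because the value usually resolves |

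The DILI clash is the most direct. Item 4 refers to 8.4.7. Section 5.1.3 says "HCC tumors are excluded from the visceral dose escalation cohort", so the non-HCC criteria apply. They begin "An elevated AST or ALT lab value that is greater than or equal to 3X the upper limit of normal" and add only bilirubin and alkaline phosphatase.

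Table 17, which governs V937 dose changes in Part I, uses three of the four triggers (not DILI) and has no such exception. A related Grade 3 ALT rise leading to hospitalization therefore requires a hold and a one-level dose reduction, yet item 4 could excuse it as a DLT.

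**2. What the other items already catch**

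- Table 14 orders permanent discontinuation for immune-related Grade 3 or 4 AST/ALT or bilirubin. If this falls in Cycle 1, item 6 applies.
- V937 is given on Days 1 and 8 of Cycle 1. A hold over Day 8 misses a dose, so item 7 applies. Item 7 cannot catch an event first arising on Days 9 to 28, which is 20 of 28 days.
- Item 5 catches a Cycle 2 delay of more than two weeks.

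The remainder is mainly related, non-immune laboratory events first arising after Day 8 without that delay. Table 3 marks the chemistry panel on Days 1 and 8 and next on Day 1 of Cycle 2, so these events surface on unscheduled tests or at the Cycle 2 draw.

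**3. An event that splits the readings**

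At DL2 or DL3, a participant has Grade 3 ALT on Day 15, related but not immune-related. The participant is hospitalized, recovers to Grade 1 by Day 36 and starts Cycle 2 that day. Cycle 2 was due on Day 29, so the delay is 36 − 29 = 7 days, below the 14 in item 5. No dose was missed and treatment was not discontinued. Item 3 read literally makes this a DLT. With item 4 governing, it meets the hospitalization trigger and is then excused as reversible.

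**4. Effect on the 9.6.2 estimate**

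Inputs: Beta(1,1) prior and 90% interval (9.6.2), n = 14 (4.1.2). Assumption: all 14 are at the RP2D and DLT-evaluable. With x DLTs the posterior is Beta(1 + x, 15 − x), with mean (1 + x)/16. The limits are its 5th and 95th percentiles.

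| x | Observed x/14 | Posterior mean | 90% interval |
|---|---|---|---|
| 0 | 0.0% | 6.25% | 0.3 to 18.1 |
| 1 | 7.1% | 12.5% | 2.4 to 27.9 |
| 2 | 14.3% | 18.75% | 5.7 to 36.3 |
| 3 | 21.4% | 25.0% | 9.7 to 44.0 |

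One reclassified event moves the observed rate by 1/14 = 7.1 points and the posterior mean by 1/16 = 6.25 points.

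**5. Effect on dose decisions (illustration only)**

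The mTPI rules are blacked out. I assumed a 30% target, a Beta(1,1) prior, decisions by unit probability mass, and seven interval settings with half-widths from 0.01 to 0.10. All seven agree on the following:

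- n = 3: 0, 1, 2 DLTs give escalate, stay, de-escalate.
- n = 6: 0, 1, 2 DLTs give escalate, escalate, stay.
- n = 14: 0 to 2 escalate, 3 to 6 stay, 7 de-escalate.

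So one event can change a decision at small n. An escalate result cannot be acted on at DL3, however, and the n = 14 changes fall where dose-finding ends.

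**The case against.** The best reply is that the lead-in already settles the matter. In a list where any item suffices, none has to govern, and an exception inside item 4 limits only item 4. The example is then a DLT under item 3 as written, and that reading is the conservative one. Overlap alone proves little, since item 1 also falls wholly within item 3.

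This is a fair reading, but it leaves the triggers and exception of item 4 with almost nothing to do. It also sits badly with the laboratory limit in item 1 and with Table 17, both of which suggest that item 4 was meant to rule laboratory values. The text leaves both readings open.

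A second reply is that *clinically nonsignificant* colours the whole exception, so a hospitalized participant or a DILI case would never be excused. That would preserve the triggers, but the list is joined by *or* and does not say so.

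Three other replies stand. The remainder is narrow. A hospitalized case would be an SAE reported to the sponsor within 24 hours, so it would not go unseen. And the study is being discontinued, so little future dosing depends on the wording.

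A reader might also infer that the ambiguity changes the dose selected, for example because going from 1 to 2 DLTs moves the upper limit from 27.9% to 36.3%, past 30%. The documents do not support that. Section 4.1.2 looks at the estimated rate closest to 30%, says only that this dose may be taken as the preliminary RP2D, and then weighs all the data. An interval crossing 30% is not a decision rule.

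**Conclusion.** The point holds as a minor defect in the definition of a primary endpoint. The exception in item 4 contradicts its treatment, duration and DILI triggers and largely its hospitalization trigger, while item 3 counts the same clinically significant Grade 3 or 4 laboratory AEs without it. Sites following the text can score one event differently.

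The firm consequence is for the RP2D estimate that 9.6.2 still requires: 6.25 points of posterior mean per reclassified event, assuming 14 evaluable participants at that dose. How many such events occurred cannot be derived from the documents, and no probability is claimed. Confidence is high for the conflict in wording. The effect on escalation is illustrative only.

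**What to change.** 1. **Item 4.** Limit the exception to clinically nonsignificant abnormalities that meet none of the four triggers, striking the *treatable* and *reversible* limbs. Any related Grade 3 or 4 laboratory value that meets a trigger is then a DLT under the list.
2. **Item 3.** Leave to the sponsor whether laboratory AEs that meet no trigger should count. Removing them would loosen the definition as literally written, which is a trade-off and not needed to cure the contradiction. The same goes for asymptomatic Grade 3 amylase or lipase rises lasting over a week, which item 3 excepts and item 4 can count.
3. **Reporting.** Leave past dose decisions as made. List every related Cycle 1 Grade 3 or 4 laboratory event in Part I with the item it was scored under. If any was excepted under item 4, also give the 9.6.2 DLT rate and 90% credible interval with it counted. If none was, the listing closes the question.

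The cost is one wording edit, one listing and possibly one extra line in the DLT table, with no new data. The downside is that the reported DLT rate may be slightly less favourable.
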